### **An SAE is defined as any untoward medical occurrence that, at any dose:**

#### **a. Results in death**

#### **b. Is life-threatening**

The term 'life-threatening' in the definition of 'serious' refers to an event in which the participant was at risk of death at the time of the event. It does not refer to an event, which hypothetically might have caused death, if it were more severe.

#### **c. Requires inpatient hospitalisation or prolongation of existing hospitalisation**

- In general, hospitalisation signifies that the participant has been detained (usually involving at least an overnight stay) at the hospital or emergency ward for observation and/or intervention that would not have been appropriate in the physician's office or outpatient setting. Complications that occur during hospitalisation are considered AEs. If a complication prolongs hospitalisation or fulfills any other serious criteria, the event is serious. When in doubt as to whether "hospitalisation" occurred or was necessary, the AE should be considered serious.
- Hospitalisation for elective intervention of a pre-existing condition that did not worsen from baseline is not considered an AE.

#### **d. Results in persistent disability/incapacity**

- The term disability means a substantial disruption of a person's ability to conduct normal life functions.

- This definition is not intended to include experiences of relatively minor medical significance such as uncomplicated headache, nausea, vomiting, diarrhea, influenza, and accidental trauma (e.g., sprained ankle) which may interfere with or prevent everyday life functions but do not constitute a substantial disruption.

**e. Is a congenital anomaly/birth defect**

**f. Other situations**

- Medical or scientific judgment should be exercised in deciding whether SAE reporting is appropriate in other situations such as important medical events that may not be immediately life-threatening or result in death or hospitalisation but may jeopardise the participant or may require medical or surgical intervention to prevent one of the other outcomes listed in the above definition. These events should usually be considered serious.
- Examples of such events include invasive or malignant cancers, intensive intervention in an emergency room or at home for allergic bronchospasm, blood dyscrasias or convulsions that do not result in hospitalisation, or development of drug dependency or drug abuse.

## Recording and Follow-up of AE and SAE

### AE and SAE Recording

- When an AE/SAE occurs, it is the responsibility of the Investigator to review all documentation (e.g., hospital progress notes, laboratory, and diagnostics reports) related to the event.
- The Investigator will then record all relevant AE/SAE information in the CRF.
- It is **not** acceptable for the Investigator to send photocopies of the participant's medical records to the clinical research organisation (CRO) in lieu of completion of the AE/SAE CRF page.
- There may be instances when copies of medical records for certain cases are requested by the CRO/Sponsor. In this case, all participant identifiers, with the exception of the participant number, will be blinded on the copies of the medical records before submission to the CRO/Sponsor for review.
- The Investigator will attempt to establish a diagnosis of the event based on signs, symptoms, and/or other clinical information. In such cases, the diagnosis (not the individual signs/symptoms) will be documented as the AE/SAE.

- The CRF will be reconciled with the safety database during and at the end of the trial. Therefore, the sites should ensure that the data entered on any SAE forms and the data entered into the CRF are consistent.

### **Assessment of Intensity**

The Investigator will make an assessment of the intensity for each AE and SAE reported during the study and assign it to one of the following categories:

- Mild: An event that is easily tolerated by the participant, causing minimal discomfort and not interfering with everyday activities.
- Moderate: An event that causes sufficient discomfort and interferes with normal everyday activities.
- Severe: An event that prevents normal everyday activities. An AE that is assessed as severe should not be confused with an SAE. Severe is a category utilised for rating the intensity of an event; and both AE and SAE can be assessed as severe.

An event is defined as 'serious' when it meets at least one of the predefined outcomes as described in the definition of an SAE, NOT when it is rated as severe.

### **Assessment of Causality**

- The Investigator is obligated to assess the relationship between study intervention and each occurrence of each AE/SAE on a 5-point scale (not related, unlikely, possible, probable, highly probable).
- The Investigator will use clinical judgment to determine the relationship.
- Alternative causes, such as underlying disease(s), concomitant therapy, and other risk factors, as well as the temporal relationship of the event to study intervention administration will be considered and investigated.
- The Investigator will also consult the Investigator's Brochure and/or Product Information, for marketed products, in his/her assessment.
- For each AE/SAE, the Investigator must document in the medical notes that he/she has reviewed the AE/SAE and has provided an assessment of causality.
- There may be situations in which an SAE has occurred, and the Investigator has minimal information to include in the initial report in the electronic CRF/EDC. However, it is very important that the Investigator always make an assessment of causality for every event before the initial transmission of the SAE data to electronic CRF/EDC.

- The Investigator may change his/her opinion of causality in light of follow-up information and send an SAE follow-up report with the updated causality assessment.
- The causality assessment is one of the criteria used when determining regulatory reporting requirements.

### **Follow-up of AE and SAE**

- The Investigator is obligated to perform or arrange for the conduct of supplemental measurements and/or evaluations as medically indicated or as requested by the Sponsor to elucidate the nature and/or causality of the AE or SAE as fully as possible. This may include additional laboratory tests or investigations, histopathological examinations, or consultation with other health care professionals.
- New or updated information will be recorded in the originally completed CRF.
- The Investigator will submit any updated SAE data to the Sponsor within 24 hours of receipt of the information.

## **Reporting of SAE**

### **SAE Reporting**

All SAEs will be recorded from signing of informed consent until the end of the study. Serious adverse events occurring after the end of the study and coming to the attention of the Investigator must be reported only if they are considered (in the opinion of the Investigator) causally related to study intervention.

Other events which must be reported in the same manner as an SAE include:

- Overdose (any dose above that specified in the protocol, not necessarily intentional)
- Abuse or misuse
- Medication error (any unintentional error in the dispensing or administration of an IMP)
- Occupational exposure (to a person other than the patient, for example spilling of IMP on hands of nurse or splashing in the eye)
- STIAMP (suspected transmission of an infectious agent via a medicinal product)

- Any AE that could be related to the protocol procedures and which could modify the conduct of the trial.

The Investigator must report any SAEs to the Sponsor **within 24 hours** of becoming aware of the event by emailing an SAE form to the Sponsor's PV department.

The Sponsor's PV department will confirm receipt within one business day. The site should re-send any report where acknowledgement of receipt is not provided.

Each episode of an SAE must be recorded on a separate SAE form. If new or amended information on a previously reported SAE becomes available, the Investigator should report this to the PV department on a new SAE form.

Where an SAE has not been reported to the Sponsor within the specified timelines, a reason for lateness must be included with the SAE form.

All SAEs will be recorded from signing of informed consent until the end of the study. Serious adverse events occurring after the end of the study and coming to the attention of the Investigator must be reported only if they are considered (in the opinion of the Investigator) causally related to study intervention.

- The primary mechanism for reporting an SAE will be using a paper SAE reporting form
- The Investigator and the Sponsor (or Sponsor's designated agent) will review each SAE report and the Sponsor will evaluate the seriousness and the causal relationship of the event to study intervention. In addition, the Sponsor (or Sponsor's designated agent) will evaluate the expectedness according to the reference document (Reference Safety Information section in the Investigator Brochure). Based on the Investigator and Sponsor's assessment of the event, a decision will be made concerning the need for further action.

### **Suspected Unexpected Serious Adverse Reactions (SUSARs)**

Any AE that is a SUSAR has additional reporting requirements, as described below.

- If the SUSAR is fatal or life-threatening, associated with study intervention, and unexpected, regulatory authorities and IECs will be notified within seven calendar days after the Sponsor learns of the event. Additional follow-up (cause of death, autopsy report, and hospital report) information should be reported within an additional 8 days (15 days total).
- If the SUSAR is not fatal or life-threatening but is otherwise serious, associated with study intervention, and unexpected, regulatory authorities and IECs will be notified within 15 calendar days after the Sponsor learns of the event.

The Sponsor will notify the Investigators in a timely fashion of relevant information about SUSARs that could adversely affect the safety of participants. Follow-up information may be submitted if necessary.

The Sponsor will also provide annual safety updates to the regulatory authorities and IECs responsible for the study. These updates will include information on SUSARs and other relevant safety findings.

### **Urgent Safety Measures (USM)**

The sponsor/sponsor's designee or investigator may take appropriate urgent safety measures (USMs) in order to protect the subjects of a clinical trial against any immediate hazard to their health or safety. This includes procedures taken to protect subjects from pandemics or infections that pose serious risk to human health.

USMs may be taken without prior authorization from the competent authority. Should the site initiate a USM, the investigator must inform the sponsor or sponsor's designee immediately.

## GLOSSARY OF ABBREVIATION

AE	Adverse Event
ATC	Anatomical Therapeutically Chemical
BMI	Body Mass Index
CCQ	Clinical COPD Questionnaire
CFR	Code of Federal Regulations
CI	Confidence interval
CIOMS	Council for International Organizations of Medical Sciences
COPD	Chronic obstructive pulmonary disease
COVID-19	Coronavirus disease 2019
eCRF	electronic Case Report Form
CRO	Contract Research Organization
CT	Computerized Tomography
DMC	Data Monitoring Committee
DRE	Disease Related Event
ECG	Electrocardiogram
EDC	Electronic Data Capture
FAS	Full Analysis Set
FDA	Food and Drug Administration
GCP	Good Clinical Practice
ICF	Informed Consent Form
ICH	International Council for Harmonization
IDMC	Independent Data Monitoring Committee
IEC	Independent Ethics Committee
IMP	Investigational Medicinal Product
IRB	Institutional Review Board
ITT	Intent To Treat
MedDRA	Medical Dictionary for Regulatory Activities
mHb	Methaemoglobin
NHS	National Health Service
NO	Nitric oxide
NO2	Nitrogen dioxide
NOx	Oxide of nitrogen
PEoT	Post End of Treatment
PR	Pulse Rate
PT	Preferred Term
PP	Per Protocol
QC	Quality Control
RTD	Recommended Therapeutic Dose
SAC	Safety Advisory Committee
SAE	Serious Adverse Event
SAP	Statistical Analysis Plan
SAS	Statistical Analysis system
SD	Standard Deviation

---

SEM	Standard Error of the Mean
SoA	Schedule of activities
SOC	Standard of Care or System Organ Class
SP	Safety population
SpO 2	Oxygen saturation
SUSAR	Suspected Unexpected Serious Adverse Reaction
SOP	Standard Operative Procedure
TEAE	Treatment-emergent adverse event
TID	Three Times Daily
TMF	Trial Master file
VAS	Visual Analogue Scale
WHO-DD	World Health Organization Drug Dictionary

## 1. INTRODUCTION

The purpose of this Statistical Analysis Plan (SAP) is to provide a more technical and detailed description of the statistical methods mentioned in the protocol of study RESP301-005:

CORVIS-Study: Community participants with COPD or bronchiectasis and at risk of Respiratory Viral Infections including SARS-CoV-2: An open-label, multicentre feasibility study of an inhaled nitric oxide generating solution (RESP301).

This analysis plan is developed based on ICH E3 and E9 guidelines and in reference to the following documents:

- the last version of the protocol (18th of November 2021, vers. 5.0)
- the annotated eCRF (13th of September 2021, vers. 1.0)
- the trial monitoring plan for Clinical Trials Sponsored by Thirty Respiratory Limited, Version 4.0, 17th of February 2022

Any significant changes from the methodology defined in the current protocol/eCRF or protocol amendments agreed after the approval of this SAP may require changes to this SAP, see section 5.13 for details.

## 2. STUDY OVERVIEW

### 2.1 Study Objectives and Hypotheses

This study is divided in two parts, a dose finding part (part 1) followed by an expansion phase (part 2):

In part 1, the maximum tolerable dose (MTD) and the recommended therapeutic dose (RTD) of a single agent RESP301 in patients with mild to moderate COPD or bronchiectasis will be determined. In an additional cohort, the safety and tolerability of administering RESP301 at the MTD with the co-administration of a short acting bronchodilator will be investigated.

In part 2, the effects on recruiting and retaining patients with COPD or bronchiectasis who have viral infection symptoms and treating these patients with RESP301 in a community setting will be investigated.

The secondary objectives of this study are:

- To assess the safety and tolerability of single doses of RESP301 in patients with COPD or bronchiectasis, who are at high risk of SARS-CoV-2 and other acute respiratory pathogens.
- To assess the safety and tolerability of single doses of RESP301 in combination with a short acting bronchodilator.
- To collect preliminary data on the efficacy of RESP301.

## 2.2 Study Design

This is a phase II, single-group, non-randomized, two-center, open-label study conducted in two parts.

In part 1 (Dose Finding Phase), eligible patients will be administered a single dose of RESP301 under clinical supervision. The first eight patients (group 1) will receive a dose of 1 ml, the next eight patients (group 2) 2 ml, the next eight patients (group 3) 3 ml, etc. until a maximum dose of 6 ml. After the completion of each dose level (treatment group) the safety data will be reviewed by the PIs and Sponsor before proceeding to the next higher dose. After the completion of all groups a safety advisory committee (SAC) will review the data from all participants and determine a Maximum Tolerated Dose(MTD) and a Recommended Therapeutic Dose (RTD).

Thereafter eight eligible patients will be administered a single dose of RESP301 at the MTD in combination with a short acting bronchodilator also under clinical supervision.

In part 2 (Expansion Phase), a minimum of 150 patients will be enrolled into the Expansion Phase and treated at the Recommended Therapeutic Dose (RTD) determined in Part 1. The expansion phase is split into three periods, a baseline visit, a dormant period (max. 12 months) and a treatment period (7 days). The first 50 patients at baseline will receive a RTD test dose on site to further investigate the safety and tolerability of RESP301.

An Independent Data Monitoring Committee (IDMC) will review this data and decide whether further RTD test doses should be administered to further patients before enrolling them into the Dormant Period or whether patients could be enrolled into the dormant period without a RTD test dose at baseline.

Female of non-childbearing potential or male  $\geq 35$  years of age, at the time of signing the informed consent with spirometry-confirmed COPD or computerized tomography (CT) proven bronchiectasis are included in the study. Further details of the inclusion/exclusion criteria are defined in sections 6.2 and 6.3 of the protocol.

Eligible patients in part 1 may be enrolled in more than one of the seven treatment groups and patients from part 1 will also be eligible to enter Part 2 of the trial.

The overall study duration for each patient will be at approximately 60 weeks, including one or more visits at a study center in parts 1/2, monthly follow-up calls, and, for those who experience an exacerbation (part 2), one week of treatment and additional monitoring calls at the beginning, during and following the treatment period.

The eight treatment groups, the number of subjects per group and the corresponding treatment labels used for the statistical evaluation are summarized in table 1.

**Table 1: Treatment Groups**

Part	Treatment group*	Label	Short label**
1	1 (N=8)	RESP301 1 ml	1ml
	2 (N=8)	RESP301 2 ml	2ml
	3 (N=8)	RESP301 3 ml	3ml
	4 (N=8)	RESP301 4 ml	4ml
	5 (N=8)	RESP301 5 ml	5ml
	6 (N=8)	RESP301 6 ml	6ml
	7 (N=8)	RESP+Vent 6 ml	R+V
2	8 (N=150)	RESP301 RTD	RTD

\* During a meeting on the 11th of January 2022 it was decided that the RTD dose is 4 ml and the MTD dose 6 ml.

\*\* Short labels may be used due to paper space requirements.

RESP301 is prepared by mixing two sterile solutions (one of NaNO2/mannitol and one of citric acid buffered to pH █) in the nebulizer. The solution is to be nebulized within 5 minutes post mixing as per the instructions given in the SoA. The inhalation of the medication should start within 5 minutes of mixing the solutions and the inhalation process should be complete within 20 minutes of starting inhalation.

An overview of the study procedures is provided in table 2 below for part 1 of the study and in table 3 for part 2, see protocol page 51, table 8-1:

**Table 2: Schedule of Study Assessments (Part 1)**

Procedure	Screen 1	Screen 2/Dosing Visit (Day 1) 	Follow-up Phone call (Day 2)
Informed Consent	X		
Inclusion and Exclusion Criteria	X	X	
Demographics	X		
Medical History	X		
Medication history and concomitant medications	X	X	X
Height, Weight and BMI	X		
Physical Examination 	X	X	
Pulmonary function test	X	X	
Vital signs	X	X	
Methaemoglobin level	X	X	
Short acting bronchodilator 		X 	
RESP301 administration		X	
Follow-up			X
AE/SAE review	X	X	X

 Only done if deemed necessary by the investigator

 Only done in the combination group, i.e., RESP301 + short acting bronchodilator (group 7)

 Screen 1 and Screen 2 may be combined if the patient has historic evidence of a FEV1/FVC ratio <0.7.

**Table 3: Schedule of Study Assessments (Part 2)**

Procedure	Screen 1	Screen 2/ Baseline Visit 	Dormant Period (monthly calls)	Pre-Treatment call (within 24-72 hrs of exacerbation onset)	Treatment Period (daily monitoring calls for 8 days)	Post Treatment Follow-up call (Day $14\pm 3$ PEoT)	Post Treatment Follow-up call (Day $28\pm 3$ PEoT)	Early withdrawal (Days 0, 14 or 28 $\pm$ 3)
Informed Consent	X	X						
Inclusion and Exclusion Criteria	X	X						
Demographics	X							
Medical History	X			X	X	X	X	X
Medication history and concomitant medications	X	X		X	X	X	X	X
Height, Weight and BMI	X							
Physical Examination 	X	X						
Pulmonary function test 	X	X						
Vital signs	X	X						
Methemoglobin level	X	X						
RESP301 administration 		X			X			
CCQ		X	X		X 	X		
Instructions of nebulizer		X		X	X			
Follow-up 			X					
Review of symptoms				X	X	X		
AE/SAE review	X	X			X	X	X	X
VAS 					X	X		

Body temperature 				X	X	X		
Treatment compliance					X			

 Patients who received a RTD test dose only and did not proceed to the dormant period, will receive a follow-up call on day 7±3 to discuss and record AEs.

 Only done if deemed necessary by the investigator

 Only done in patients who received a RTD test dose at the Baseline visit

 At baseline a single RTD dose for patients who were assigned to test dose and at the treatment period TID for 1- 7 days in patient with an exacerbation

 Done at Day 1 and Day 7

 Patients reminded to contact the study team if they experience exacerbation symptoms

 Daily during the treatment period, and if not recovered by end of treatment, continued until recovery or Day 14 post end of treatment

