	
To be evaluated on the full cohort, and separately in the sub-cohort of those who test positive for SARS-CoV-2:
 

• Safety and tolerability of RESP301 in terms of:

○ % of participants able to tolerate the test dose in Parts 1(a), 1 (b) and 2

○ Total counts and cumulative incidence of:

▪ Adverse Events (AEs)

▪ Serious Adverse Events (SAEs)

▪ Suspected Unexpected Serious Adverse Reactions (SUSARs)

▪ Severe AEs

▪ Treatment-related AEs/SAEs

• Feasibility in terms of percentage of patients who, having experienced and correctly reported an exacerbation, receive the treatment within 48 hours of reporting their exacerbation

• Efficacy of RESP301 in terms of:

○ % of participants recovered by Day 7 and Day 14 post starting treatment

○ time to recovery (days until patient feels all their symptoms are back to their usual baseline (all VAS = 0))

○ preventing exacerbation-related hospitalisation and/or death

○ change in CCQ score

Duration of participation in the study	The overall study duration for each participant will be at most approximately 60 weeks, including one or more visits at a study centre in Parts 1/2, monthly follow-up calls, and, for those who experience an exacerbation, one week of treatment and additional monitoring calls at the beginning, during and following the treatment period.
Study population	Participants will be adult patients with spirometry-confirmed COPD or computerised tomography (CT) proven bronchiectasis, recruited from secondary and primary care sites in the UK.
Sample size	
Part 1(a):
 
We aim to recruit up to 48 participants. All participants who complete Part 1a, will also be eligible to enter Part 2 of the trial.
 
Part 1(b):
 
We aim to recruit 8 participants who are not experiencing an exacerbation. These participants will receive a short acting

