### **Treatment period**

A patient entered into the dormant period who experiences exacerbation symptoms for at least [REDACTED] will be eligible to enter the Treatment period. Patients will be instructed to contact the study team as soon as practicable to allow a study interaction to be undertaken remotely (via video link, if possible), within [REDACTED] of onset of at least one of the following:

- Fever (>38.0°C),
- Systemic malaise,
- Increased cough or wheeze,
- Increased sputum volume or increased purulence.

During the remote visit the patient's symptoms will be discussed and if the patient is willing to continue in the study, [REDACTED]

Note that if COVID-19 is suspected, the patient will be advised to follow the prevailing NHS guidance on testing for COVID-19 taking into account any specific recommendations for patients with COPD or bronchiectasis. Where serial SARS-CoV-2 swabs are undertaken, data will be collected for analysis.

During the treatment period, [REDACTED], at home/ community setting, patients will be asked to:

- Administer RESP301 [REDACTED] at the dose determined in Part 1 of the study (RTD).
- Take daily temperature measurements
- Complete a daily diary to record treatment doses

- Attend a daily call with study coordinator to check compliance, assist with issues with product, and report any AEs and changes to medications or medical history, including COVID-19 test results, if available.

[REDACTED]

[figure not shown]
[REDACTED]

[REDACTED]

In summary, the Part 2 of the study will involve the following visits/calls and study phases:

- Screening/Baseline Visit (Day 0), including test dose if required
- Dormant period (from Day 1, until the first exacerbation or end of study at week 52)
  - During this phase, monthly calls will be conducted
- Remote study visit ([REDACTED])
- Treatment period ([REDACTED])
  - During this phase, daily monitoring calls will be conducted; additionally, a call to collect [REDACTED] data will be conducted 1 day PEoT
- Follow-up period ([REDACTED])
  - Patients who still experience exacerbations symptoms at the end of the [REDACTED] treatment period will be asked to continue the study diary until symptoms return to baseline level (i.e. VAS score = 0), or until [REDACTED] after the end of treatment, whichever is sooner.
  - All patients will receive a follow-up call [REDACTED]
  - All patients will receive a final follow-up call [REDACTED]

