## **5. METHODS OF ANALYSIS AND PRESENTATION**

### **5.1 General Principles**

The statistical analysis will be performed using the validated software package SAS version 9.4 or higher (SAS Institute Inc., Cary, NC 27513, USA).

All recorded and derived variables will be presented by treatment group and visits (if appropriate) using descriptive summary tables (continuous data: sample size, mean, standard deviation (SD), minimum, median, maximum; categorical data: sample size, absolute and relative frequency).

The mean and median will be presented to one more decimal place than the raw data. The SD will be presented to two more decimal places than the raw data. The percentages will be presented to 1 decimal place. In all the summaries, the treatment groups will be displayed in the following order: part 1 (RESP301 1 ml, 2 ml, ...6 ml, RESP+Vent 6 ml) and then part 2.

For all parameters, baseline is defined as the last available pre-treatment value (i.e. the last non-missing value available before study drug administration. In general, missing data will be treated as missing and no attempts will be made to impute values for missing data.

No formal interim efficacy analyses are planned in this study; however, several safety interim analyses by the Safety Advisory Committee (SAC) will be performed as detailed in the protocol, see section 7.7 for part 1 and an Independent Data Monitoring Committee (IDMC) will review the safety data on an ongoing basis as described in the DMC charter, see section 10.6 of the protocol.

Subjects who did not receive any study medication (screening failures) will be listed separately and not presented in any table or figure, except in the patient's disposition table.

The versions of the following international dictionaries (MedDRA version 26.1 and WHO DD, version 2024) will be used for medical coding:

Adverse events: Medical Dictionary for Regulatory Activities (MedDRA).

Medical Histories: Medical Dictionary for Regulatory Activities (MedDRA).

Medications: World Health Organization (WHO) Drug Dictionary including Anatomical Therapeutic and Chemical (ATC) classification.

If a medication in the drug dictionary (DD) table is associated with more than one ATC code, the first ATC code will be assigned to that medication.

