## **VAS Scores**

For each parameter will be summarized by treatment group using descriptive statistics at each time point.

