## 15.2 Efficacy Results

Table 1.1	Summary of primary endpoints, part 2 – FAS/PPS set
Table 1.2	Summary of secondary endpoints – FAS/PPS set
Table 1.3	Summary statistics of spirometry over time – FAS/PPS set
Table 1.4	Summary of VAS scales – FAS/PPS set
Table 1.5	Summary statistics of explorative/sub-group analyses, if any – FAS/PPS set

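### After treatment VAS is recorded only until recovery, so the SAP's post-treatment VAS summaries leave out recovered patients and overstate symptoms in the treated group

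*SAP*

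**What the plan says.** - **Collection.** SAP Table 3 attaches footnote 7 to the VAS row: "Daily during the treatment period, and if not recovered by end of treatment, continued until recovery or Day 14 post end of treatment". The row is marked for the treatment period and for the Day 14 PEoT call, so the restriction covers that call too. Protocol 5.1 (Treatment period) applies the same rule to the diary: patients still symptomatic at the end of treatment are "asked to continue the study diary until symptoms return to baseline level (i.e. VAS score = 0"), up to a time limit.
- **Recovery.** The synopsis endpoint time to recovery counts "days until patient feels all their symptoms are back to their usual baseline (all VAS = 0"). Whether a post-treatment VAS exists therefore depends on the VAS value itself.
- **Analysis.** SAP 5.11, VAS Scores: "For each parameter will be summarized by treatment group using descriptive statistics at each time point". The output is Table 1.4 in SAP 15.2, "Summary of VAS scales", on the FAS and PPS.
- **Missing data.** SAP 5.1: "In general, missing data will be treated as missing and no attempts will be made to impute values for missing data". Protocol 10.4.1 likewise does not replace missing values unless it says otherwise. The SAP states no exception for VAS.

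**The concern.** On the last treatment day, everyone still under observation contributes a VAS. At the next assessment, all patients who had already reached 0 are gone, and each later recovery removes another patient whose last score was 0. These absences are not ordinary missing data, because the design causes them and the last value is known. A mean over whoever still records is a mean over a group chosen for still having symptoms.

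The change in who is counted falls exactly where RESP301 stops. A rise there could be read as rebound after treatment, and a single-arm study has no comparator in which the same artefact would show. SAP 3.1 does not list the protocol's recovery endpoints (percent recovered by Day 7 and Day 14, time to recovery). Table 1.4 is therefore the only VAS summary table the SAP names, and nothing beside it would correct the impression.

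**Working it through.** The documents give no VAS scale, scores or recovery share, so there is no figure to reproduce. The direction follows from the rules; every size below rests on stated assumptions.

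**1. First assessment after treatment.** Let r be the share of treated patients recovered by the last treatment day, m the mean VAS of the rest on that day, and d the proportional fall in that mean by the next assessment.

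- Reported mean, last treatment day: (1−r)·m, since the recovered score 0.
- Reported mean, next assessment: (1−d)·m, since the recovered no longer record.
- Change: factor (1−d)/(1−r). The reported mean rises if and only if d < r.
- Mean over all treated patients at that assessment, if the recovered stay at 0: (1−r)(1−d)·m. The reported mean is too high by 1/(1−r), whether it rises or falls.

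| r (assumed) | d (assumed) | Factor on reported mean | Overstatement 1/(1−r) |
|---|---|---|---|
| 20% | 30% | 0.70/0.80 = 0.87 | 1.25 |
| 20% | 20% | 0.80/0.80 = 1.00 | 1.25 |
| 40% | 10% | 0.90/0.60 = 1.50 | 1.67 |
| 60% | 10% | 0.90/0.40 = 2.25 | 2.50 |

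**2. Worked example.** Take 30 treated patients (the number SAP section 4 expects to exacerbate) and an assumed 0–10 scale. On the last treatment day 18 are at 0, 6 at 1.0 and 6 at 6.0. The middle six then record 0 and stop. The last six go to 5.5 and then 5.0.

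| Assessment | Reported mean (n) | Mean over all 30 |
|---|---|---|
| Last treatment day | (6×1.0 + 6×6.0)/30 = 1.4 (30) | 1.4 |
| First after treatment | (6×0 + 6×5.5)/12 = 2.75 (12) | 33/30 = 1.1 |
| Second after treatment | (6×5.0)/6 = 5.0 (6) | 30/30 = 1.0 |

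Nobody worsens, yet the reported mean more than triples. The six zeros at the first post-treatment assessment show that a patient who recovers after treatment contributes one 0 before leaving. The group described is therefore those not recovered at the *previous* assessment.

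**3. Simulation over a range of recovery speeds.** 2,000 runs of 30 patients. Assumptions: one VAS on a 0–10 scale, starting values uniform from 3 to 9, linear fall to 0 with no relapse, log-normal recovery time (log SD 0.5), Day 8 as last treatment day, daily recording afterwards until the first 0. Day 22 corresponds to Day 14 PEoT; its reported mean averages the runs in which anyone still records.

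| Median days to recovery | Recovered by Day 8 | Reported mean, Day 8 → 9 | All-30 mean, Day 8 → 9 | Runs rising on Day 9 | Day 22: reported (average n) vs all 30 |
|---|---|---|---|---|---|
| 6 | 63% | 0.60 → 1.10 | 0.60 → 0.41 | 99% | 0.65 (0.2) vs 0.01 |
| 8 | 39% | 1.20 → 1.48 | 1.20 → 0.90 | 91% | 0.78 (1.0) vs 0.03 |
| 10 | 24% | 1.79 → 1.87 | 1.79 → 1.43 | 64% | 0.93 (2.4) vs 0.08 |
| 14 | 8% | 2.74 → 2.58 | 2.74 → 2.37 | 15% | 1.19 (7.1) vs 0.28 |

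A rise on some post-treatment day occurred in 97–100% of runs. The overstatement holds in every row; the jump on the first day does not.

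**The case against.** - **Visibility.** SAP 5.1 prints the sample size with every continuous summary, so a drop in n would stand beside the mean. This is true and helps. But n does not say that the absent patients had scored 0, and it does not correct the mean.
- **Undefined time points.** SAP 5.11 does not say that daily post-treatment entries will be tabulated, and Table 3 has one post-treatment VAS column, the Day 14 PEoT call. This stands. The day-after jump presupposes a daily post-treatment table. The Day 14 value is selected in the same way regardless.
- **Not a ban on imputation.** A reader might infer that the SAP forbids setting recovered patients to 0. Its sentence opens with a general qualifier, and protocol 10.4.1 leaves room for exceptions. The protocol's own efficacy definitions in 10.4.3 are blacked out, so one can say only that the SAP states no rule.
- **Limited consequence.** VAS means are not a listed endpoint in the synopsis or SAP 3.1, and the study is descriptive. The protocol's recovery endpoints are free of this bias. CCQ, which has a symptom domain, is scheduled at Days 1 and 7 and Day 14 PEoT without footnote 7. This limits the weight of the point but does not repair Table 1.4.
- **Setting recovered patients to 0 is itself an assumption.** It presumes no relapse, which favours the treatment in an uncontrolled study. This stands, so the fix should not rest on that step alone.

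**Conclusion.** The point holds. As written, post-treatment VAS summaries, including Day 14 PEoT, describe patients not recovered at their previous assessment and overstate the symptom level of the treated group. If recovered patients stay at 0, the overstatement at the first post-treatment assessment is 1/(1−r), for example 1.25-fold at r = 20% and 1.67-fold at r = 40%. It grows as more patients leave the record.

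A reader might infer that the table must show worsening when RESP301 stops, whatever the patients' course. The rules do not support that: the first post-treatment mean rises only if d < r, and with r = 20% and d = 30% it falls to 0.87 of its former value.

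Means within the treatment period are not affected by this rule. The direction rests on the documents; the sizes rest on assumed recovery shares and VAS values. This should be settled before Table 1.4 is produced, but it does not touch the primary endpoints.

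**What to change.** In SAP 5.11 and Table 1.4:

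1. Present observed VAS means for the treatment period only.
2. For each post-treatment time point, name the time point and report the number and percent recovered (all VAS = 0) among treated patients with known status.
3. Give post-treatment VAS summaries with patients whose diary stopped because all VAS = 0 set to 0. Leave patients who stopped for any other reason missing and outside that denominator.
4. Show three counts at each time point: recorded, set to 0 as recovered, and missing.
5. Label any observed-only post-treatment mean as describing patients not yet recovered.
6. State the assumption that recovered patients stay at 0, and list any relapse found at the Day 14 PEoT symptom review, which Table 3 schedules without footnote 7.

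In the worked example the summaries then read 1.4, 1.1, 1.0 instead of 1.4, 2.75, 5.0.

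The cost is SAP wording and one derivation rule, with no new data. The downside is the no-relapse assumption. A single review at Day 14 PEoT can check it only in part, because a brief relapse in between would be missed and recovered patients record no VAS there.
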